11.2 Management of Reactions to ALD403

There are no specific antidotes to ALD403.

Each medical emergency should be treated appropriately by the Investigator using proper standard of care, according to their typical clinical practice and local guidelines for that emergency condition. Emergency equipment and medication for the treatment of these potential adverse events must be available for immediate use.

Should a medical condition arise that the Investigator believes is related to the Investigational Product, clinical judgment should be used to provide the appropriate response including the consideration of discontinuation of Investigational Product.

If a subject experiences a potential systemic allergic reaction as assessed by the PI, the site will collect additional blood specimen(s) using the anaphylactic kit (unscheduled kit Type E) at the time of the event as per the PPD laboratory manual. This assessment includes serum histamine, serum tryptase, immunoglobulin E, and complement components.

As a guideline, if a site does not have a formal "crash cart", the following should be considered as a requirement at the site:

- Clinical personnel should be CPR certified
- Clinic should have an automated external defibrillator

The site should have the following emergency medications available: antihistamines, bronchodilators, IV saline, corticosteroids, acetaminophen, and epinephrine.

12 Assessment of Efficacy, Pharmacokinetics and Immunogenicity

12.1 Efficacy

12.1.1 eDiary

Subjects will complete a daily headache eDiary from the time of screening to Week 48. The diary should be completed each trial day whether or not the subject had a headache. These daily entries record if the subject took acute migraine medication on that day. The compliance data from the eDiary will be made available to the trial site for review. Sites are to review the diary results with the subject and if the subject has not completed the diary daily, counsel the subject on the importance of daily completion of the diary.

The eDiary data from the 28 days following screening visit will be used to determine eligibility criteria, and the baseline migraine and headache results.

12.1.2 Endpoints

Headache episodes will be self-reported by the subject. An episode is a single headache event that the subject reported as having a start and an end and which lasts at least 30 minutes. The term headache will encompass both headaches and migraine headaches. The migraine and headache endpoints will be summarized in four week, twelve week and the twenty-four week interval. Specifically, migraine and headache endpoints will be summarized for the four week intervals: Weeks 1-4, 5-8, 9-12, 13-16, 17-20, 21-24, ... 44-48, the twelve week intervals 1-12, 13-24, 25-36, 37-48 and Weeks 1-24, 25-48.

Migraine Day

A migraine day is defined as any day with a headache that meets the migraine or probably migraine characteristics as outlined in Section 7. Specifically, a migraine is defined as a self-reported headache which:

- 1. Lasted 4 72 hours
- 2. had at least 2 of the following
 - a. Unilateral location
 - b. Pulsating quality
 - c. Moderate or severe pain intensity
 - d. Aggravation by or causing avoidance of routine physical activity
- 3. had at least 1 of the following
 - a. Nausea and/or vomiting
 - b. Photophobia and phonophobia

A probable migraine is a headache that meets only 2 of the above criteria.

Frequency, Change and Percent Change of Migraine Days / Headache Days

The frequency of migraine days is the number of migraine days within four week intervals and the average four week frequency in twelve and twenty-four week intervals. Change from baseline is the difference in frequency between baseline and the counts within these four week intervals. The 12 and 24 week change is the difference in the frequency between baseline and

the average of the, 4 week intervals. The percent change is 100 times the ratio of the change and the baseline frequency. Similar measures will be produced based upon headache frequency.

Migraine/ Headache Responder Rate

Three responder rates will be utilized: 50%, 75% and 100%. A responder is a subject who achieves a \geq 50% reduction, \geq 75% reduction, or 100% reduction in migraine days, respectively. These reductions will be evaluated by comparing the baseline frequency of migraine days to the migraine frequency in four week intervals.

Results from these four week intervals will be combined to produce 12 and 24 week responder endpoints. A responder will be a subject who achieves the specified percent reduction in migraine headache days within these intervals based upon the average change from baseline measures.

Migraine Hours / Headache Hours

Migraine hours are the sum of the duration of migraines within four week intervals, and the average four week duration within 12 and 24 week intervals. Headache hours are similarly defined but include all headaches. Subjects with no migraines/headaches will have a duration of zero.

Migraine Attack / Headache Episode

A migraine attack is defined as 1 continuously recorded migraine. One attack may result in multiple migraine days. Headache episodes are similarly defined.

Migraine / Headache Severity

Headache severity will be collected on a 3 point scale: mild pain, moderate pain, severe pain. Subjects with no migraines/headaches will be included with a rate of zero.

Acute Medication Usage

The percent of migraines and headaches with acute medication usage will be summarized. Subjects with no migraines/headaches will be included with a rate of zero.

Acute Migraine Medication Usage

The number of days within 4 week intervals that subjects used acute migraine medication (i.e. triptan or ergotamine) will be summarized in 4, 12 and 24 week intervals. The 12 and 24 week results will be the average of the individual 4 week results that make up those wider intervals (e.g. the secondary endpoint of Weeks 1-12 will be the average of the Weeks 1-4, 5-8 and 9-12 results). The change from baseline for these measures will be the difference between the post baseline interval and baseline.

Percentage of subjects with a migraine on the day after dosing

The percent of subjects with a migraine on the day after first dose will be summarized.

Time to First Migraine

Time to the first migraine after dosing will be analyzed based upon the migraine data entered into the eDiary.

SF-36 Health Survey (SF-36 v2.0)

The SF-36 v2.0 is a health survey containing 36 questions consisting of eight scaled scores to measure quality of life over the past 4 weeks, see Appendix 15.3. The eight sections measured are vitality, physical functioning, bodily pain, general health perceptions, physical role functioning, emotional role functioning, social role functioning, and mental health.

EQ-5D-5L

The EQ-5D-5L is a descriptive system of health-related quality of life states consisting of five dimensions/questions (mobility, self-care, usual activities, pain/discomfort, anxiety/depression) each of which can take one of five responses. The responses record five levels of severity (no problems/slight problems/moderate problems/severe problems/extreme problems) within a particular EQ-5D dimension. The EQ-5D-5L additionally includes a VAS scale. Each item will be summarized separately.

Allodynia Symptom Checklist (ASC-12)

The ASC-12 includes 12 questions about the frequency of various allodynia symptoms in association with headache attacks. For individuals with more than one type of headache, questions are directed to the "most severe type of headache." Each item is measured on a Likert type scale option with response categories: "Does not apply to me", "never," "rarely," "less than half the time," and "half the time or more," see Appendix 15.5. ASC items were scored as 0 (i.e., never, rarely, or does not apply to me), 1 (less than half the time), and 2 (half the time or more), yielding scores that ranged from 0 to 24. In this study, if a single item is missing it will be scored as a zero. If more than one item is missing the total score will be missing. The interpretation of the total score is provided below.

Score Range	Allodynia
0-2	None
3-5	Mild
6-8	Moderate
≥9	Severe

Brush Allodynia

Dynamic mechanical brush allodynia will be tested by lightly brushing a 10 by 10 cm gauze pad bilaterally, 1-2 cm over each eyebrow at a rate of 2/second, for a total of 10 times. ¹⁴ For each side of their forehead, subjects will be asked to assess the degree of pain elicited by the gauze on a scale of 0 to 10 with 0 being no pain and 10 being the worst imaginable pain. ¹⁵

12.2 Pharmacokinetics

The concentrations of Free ALD403 will be measured in plasma from all ALD403-treated subjects using validated assay methods. The PK analysis will include evaluations of concentration-time profiles for Free ALD403 at the following times: pre-dose on Day 0, and Weeks 4, 8, 12, 16, 20, 24, 36, 48 and 56. Plasma collected at Week 4 from all placebo-treated subjects will be analysed for the potential presence of Free ALD403 using validated assay methods.

Additional sample handling, processing, storage, labelling and shipping instructions will be provided to the site in a laboratory manual.

If a subject terminates early from the clinical trial, all efforts will be made to collect blood samples to analyse for Free ALD403 unless consent has been withdrawn.

12.3 Immunogenicity

Serum blood samples will be taken pre-dose on Day 0, and Weeks 4, 8, 12, 16, 20, 24, 36, 48 and 56 to test for antibodies to ALD403. The immunogenicity will be assessed in serum from all ALD403-treated subjects using validated assay methods. Immunogenicity will not be assessed in placebo subjects.

If a subject terminates early from the clinical trial, all efforts will be made to collect blood samples to analyze antibodies against ALD403 unless consent has been withdrawn. For any samples that are positive for anti-ALD403 antibody, there may be additional testing to characterize the potential for neutralizing (NAb) ALD403 activity. Subjects who test positive for specific anti-ALD403 antibodies at the time of the last study visit will be asked to provide up to 2 additional blood samples for immunogenicity testing at approximately 3 month intervals for up to 6 months.

Additional sample handling, processing, storage, labelling and shipping instructions will be provided to the site in a laboratory manual.

[figure not shown]
13 Statistical Considerations

13.1 Decision Rule

A serial procedure will be used to account for multiplicity of dose level for the primary endpoint and the secondary endpoints. This procedure will start with the 300 mg vs placebo comparison for the primary endpoint. If this is significant, testing will continue to a subset of the key secondary endpoints for 300 mg (first the Weeks 1-4 75% responder endpoint, then the Weeks 1-12 75% responder endpoint, and then the Weeks 1-12 50% responder endpoint). The procedure will then move on to the primary endpoint for the 100 mg group and subsequently to the same subset of key secondary endpoints as tested for the 300 mg dose. The procedure will then move on to the remaining key secondary endpoint for 300 mg and 100 mg (i.e., percentage of subjects with a migraine on the day after dosing). Only if all of these secondary endpoints

reach statistical significance will the 30 mg group be tested. This testing algorithm is presented below.

Statistical testing will be conducted at the 5% alpha level.

13.2 Sample Size

The planned sample size for this study is 800 randomized and treated subjects. These subjects will be allocated into 4 treatment groups in a 1:1:1:1 ratio. Pair-wise testing of each ALD403 group vs. placebo will be performed. Two hundred subjects per group provides at least 95% power for each change in frequency of migraine days (Weeks 1-12) test individually assuming a treatment effect of at least 1 day and a common standard deviation of 2.7 days or less. Ninety percent power is retained for standard deviations up to 3 days. For the key secondary 75% responder rates endpoints 95% power is achieved for the pair-wise comparisons assuming rates of 24% for placebo and 42% for ALD403. For the 50% responder rate endpoints 95% power is achieved for the pair-wise comparisons assuming rates of 50% for placebo and 68% for

ALD403. For the percentage of subjects with a migraine on the day after dosing endpoint, 95% power is achieved for pair-wise comparisons assuming rates of 15% for placebo and 4% for ALD403.

These sample size calculations have been performed using Pass 2008 and are based upon t-tests and Chi-squared tests that should approximate the ANCOVA and CMH tests, respectively. ¹⁶

13.3 General Considerations

13.3.1 Definition of Baseline

Baseline for migraine and headache endpoints will be based upon the data recorded in the headache eDiary during the 28-days following screening. For other variables, the baseline assessment will be the latest available valid measurement taken prior to the administration of Investigational Product. This will generally be Day 0.

13.3.2 Handling of Missing Data

Summary statistics will be reported based upon observed data except for the diary data which will utilize the imputation outlined below. Additionally, if the start date of an AE or concomitant medication is incomplete or missing, it will be assumed to have occurred on or after the intake of trial medication, except if an incomplete date (e.g., month and year) clearly indicates that the event started prior to treatment.

Summary statistics will be reported based upon observed data except for the diary data which will utilize the imputation outlined below. Additionally, if the start date of an AE or concomitant medication is incomplete or missing, it will be assumed to have occurred on or after the intake of trial medication, except if an incomplete date (e.g., month and year) clearly indicates that the event started prior to treatment.

Subjects who do not complete the eDiary daily will have missing data. It is expected that most missing diary data will be sporadic. If the diary has been completed at least 21 days in a 28 day interval, then normalization will be used. The results will be normalized to 28 days by multiplying the observed results by the inverse of the completion rate (i.e. if a subject does not complete the diary on 5 days they will have completed the diary on 82% of the days and the normalized results will be the observed results times 1.22). If the diary has been completed on less than 21 days in the 28 day interval then the results for the 28 day interval will be a weighted

function of the observed data for the current four week interval and the results from the previous interval. The weights will be proportional to how many days the diary was completed and will provide greater weight to the results from the current interval as the diary completion rate increases. Specifically, the results will be derived as

$$28(WX_c + (1-W)X_p),$$

where W is the days the diary was completed/20, X_c is the available average daily results for the current interval and X_p are the average daily results for the previous interval.

13.3.3 Populations to be Analyzed

The populations to be analyzed are as follows:

Full Analysis Population: Randomized subjects who received Investigational Product/placebo. Subjects will be summarized within the treatment group to which they were randomized. This population will be used for efficacy analyses.

Safety Population: Includes all subjects who received Investigational Product/placebo. Subjects will be summarized within the treatment group for which they actually received treatment. This population will be used for the safety analyses.

13.4 Statistical Methods

Continuous variables will be summarized with mean, median, standard deviation, minimum, and maximum. Categorical variables will be summarized with frequency and percentage.

13.4.1 Subject Disposition, Demographics and Baseline Characteristics

An accounting of all randomized trial subjects by disposition will be presented. This summarization will include a summary of all subjects who have received trial drug. Demographic, baseline characteristics, migraine history and concomitant medications (coded by the World Health Organization Drug Dictionary) will be summarized descriptively by treatment group.

13.4.2 Efficacy Analyses

Efficacy endpoints will be summarized with descriptive statistics. The migraine and headache endpoints will be summarized by four, twelve and twenty-four week intervals with the remaining endpoints being summarized by study week.

Primary Efficacy Analyses

Hypothesis testing will be performed for the primary endpoint: change from baseline in migraine days from Weeks 1-12. This endpoint will be calculated as outlined in Section 12.1.2 and will utilize the missing data rules provided in Section 13.3.2. The hypotheses tested are

$$H_o$$
: $\Delta_{plb} = \Delta_{403}$ H_a : $\Delta_{plb} \neq \Delta_{403}$

where Δ_{403} is the change in migraine days for subjects in the ALD403 treatment arm and Δ_{plb} is similarly defined for the placebo subjects. The change from baseline is expected to be negative as migraines are being reduced. While the test outlined above is two sided, as is the alpha level used for this study (i.e. 5%), clinically relevant results require a larger reduction of migraines on the ALD403 arms.

An ANCOVA model will be used to test for a difference between treatment arms. This model will include the change from baseline measure as the response variable. Treatment and the stratification variable: baseline migraine days (continuous predictor) will be the independent variables.

Secondary Efficacy Analyses

Summary statistics including confidence interval for the treatment differences will be used to summarize the results for the secondary endpoints. Testing will be performed for the key secondary endpoints and for the change in acute migraine medication days endpoint. For the key secondary endpoints (responder rates and percentage of subjects with a migraine on the day after dosing) this testing will utilize a CMH/extended CMH test. The tests will be stratified by the randomization stratification factor. The change in acute migraine medication day endpoints will be tested using an ANCOVA model similar to the one used for the primary endpoints: change from baseline measure as the response, treatment and baseline acute migraine medication days as

independent variables. The time to first migraine analysis will be descriptively summarized based upon Kaplan-Meier methods.

The missing data rules provided in Section 13.3.2 will be used for the key secondary endpoints except for the percentage of subjects with a migraine (prevalence) on the day after dosing endpoint. Subjects who did not complete the diary on the day following dosing will be included in the prevalence rate calculation based upon their month 1 daily migraine rate. Hence, subjects with a migraine will be included in the rate calculation as a value of 1, subjects who completed the diary and did not have a migraine will be included as a zero and subjects who did not complete the diary will be included with a value between 0 and 1 equal to the number of month 1 migraine days / 28.

13.4.3 Pharmacokinetic Analyses

Analysis of Drug Concentrations

The concentrations of Free ALD403 will be listed and summarized by time point and dose group, and descriptive statistics will be provided. In this analysis, concentrations below the lower limit of quantification (LLOQ) will be set to zero.

Plots of the individual concentrations of Free ALD403 will be presented over time (linear and log scales). Plots of the mean or median concentration will be presented over time (linear and log scales). When the scale is linear, concentrations below the lower limit of quantification will be set to zero. In the log-scaled figures, concentrations below the LLOQ will be imputed as LLOQ/2. Population pharmacokinetic analysis will be performed on the results for Free ALD403 concentrations obtained during this study in combination with the results from previous studies of ALD403 in normal subjects and migraine patients.

13.4.4 Safety Analyses

13.4.4.1 Adverse Events

The incidence of all AEs and treatment-related AEs will be tabulated by treatment received.

These AEs will be classified by system organ class and preferred term using the Medical

Dictionary for Regulatory Activities (MedDRA). For incidence reporting, if a subject reported

more than 1 AE that was coded to the same preferred term/system organ class, the subject will be

counted only once for that specific preferred term/system organ class. Events recorded between the time the informed consent is signed and the first Investigational Product administration will be listed.

An overview of AEs, which includes subject incidence of AEs, treatment-related AEs, SAEs, deaths, and AEs leading to discontinuation, will be presented. For AEs presented by severity, the worst severity during the clinical trial will be presented for each subject.

The subject incidence of AEs and treatment-related AEs will be summarized by system organ class and preferred term.

13.4.4.2 Serious Adverse Events

All SAEs will be listed and summarized in a similar manner to AEs.

13.4.4.3 Clinical Laboratory Results

Clinical laboratory values will be measured by a central laboratory.

Summary statistics for actual values and for changes from baseline will be tabulated for clinical laboratory results by scheduled visit. Subjects with clinical laboratory values outside of the normal reference range at any post-baseline assessment will be summarized. Shifts from baseline clinical laboratory values based upon the normal range and will be tabulated. Subjects developing an antibody response will be listed.

13.4.4.4 Electrocardiogram (ECG) Results

The observed data at baseline and change from baseline for each measurement day will be summarized with descriptive statistics.

13.4.4.5 Vital Signs

The observed data at baseline and change from baseline for each measurement day will be summarized with descriptive statistics.

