5.2 Background

According to the International Classification of Headache Disorder, migraine is a common disabling primary headache disorder manifesting in attacks lasting 4 to 72 hours. Migraine headaches range from moderate to very severe and are debilitating. Episodic migraine affects 17 percent of women and 6 percent of men. Migraine frequency is divided into episodic and chronic episodic migraine is characterized by <15 migraine days and chronic migraine by ≥15 headache days per month of which 8 or more must be migraine days. All migraine types significantly affect the physical, psychological, and social well-being of patients, and can impose serious lifestyle restrictions. Each year lost work time and diminished productivity from migraine costs American employers \$225.8 billion. Forty percent of adults with episodic migraine and all patients with chronic migraine might benefit from preventive medication; yet, only about 12 percent of adults with migraines take preventive medication. This is largely due to poor tolerability and/or lack of efficacy of currently marketed drugs for the prevention of migraine. There is therefore a need for new therapeutic alternatives¹.

CGRP is a member of the calcitonin family of peptides, which in humans exists in two forms, α -CGRP and β -CGRP. α -CGRP is a 37-amino acid peptide and is formed from the alternative splicing of the calcitonin/CGRP gene located on chromosome 11. The less-studied β -CGRP differs in three amino acids (in humans) and is encoded in a separate gene in the same vicinity of the genome.

CGRP is one of the most abundant peptides produced in both peripheral and central neurons. It is the most potent peptide vasodilator and can function in the transmission of pain. In the spinal cord, the function and expression of CGRP may differ depending on the location of synthesis. CGRP is derived mainly from the cell bodies of motor neurons when synthesized in the ventral horn of the spinal cord and may contribute to the regeneration of nervous tissue after injury.

Conversely, CGRP is derived from dorsal root ganglion when synthesized in the dorsal horn of the spinal cord and may be linked to the transmission of pain. In the trigeminal vascular system, the cell bodies on the trigeminal ganglion are the main source of CGRP where it is thought to have a role in cardiovascular homeostasis and nociception.²

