8.2 Exclusion Criteria

A subject who meets any of the following criteria will be excluded from the trial:

- 1. Confounding pain syndromes, e.g. fibromyalgia, complex regional pain syndrome or any pain syndrome that requires regular analgesia
- 2. Psychiatric conditions that are uncontrolled and untreated, including conditions that are not controlled for a minimum of 6 months prior to screening
- 3. Known or suspected Temporo-Mandibular Disorders (TMD)
- 4. History or diagnosis of complicated migraine (ICHD- II, 2004 Section 1 ¹¹), chronic tension-type headache, hypnic headache, cluster headache, hemicrania continua, new daily persistent headache, migraine with brainstem aura, sporadic and familial hemiplegic migraine
- 5. Unable to differentiate migraine from other headaches
- 6. Have present or previous malignancies, except:
 - Subjects with a history of squamous or basal skin cell carcinoma with excision for cure
 - Subjects with a history of breast or cervical cancer ≥ 10 years since diagnosis/treatment without evidence of recurrence
- 7. Cardiovascular disease (hypertension, ischemic heart disease), neurological disease, cerebrovascular disease, diabetes, or Raynaud's disease, life-threatening allergy (e.g, anaphylaxis); if questions arise, the Investigator should contact the Medical Monitor for guidance

- 8. Have a clinically significant abnormal ECG at screening or pre-dose on Day 0. An alert for a clinically significant abnormality will be set at the following interval values:
 - RR < 460 msec (or HR > 130 bpm)
 - RR > 1700 msec (or HR < 35 bpm)
 - QRS > 180 msec
 - QTcF > 500 msec (or any other QTc method if QTcF is not utilized)
- 9. Have any clinically significant concurrent medical condition as shown by, but not limited to:

Hepatic

• ALT \geq 2 x ULN; AST \geq 2 x ULN

Hematology

- Hemoglobin < 10 g/dL
- Absolute neutrophil count < 1000cells/μL
- Platelet count $< 100,000 \text{ cells/}\mu\text{L}$ (patients with 75,000-100,000 cells/ μL can be considered for enrollment if there are no comorbid conditions; contact Medical Monitor prior to enrollment)

Renal

- Creatinine > 2.0 mg/dL
- 10. Systolic blood pressure (BP) 140 mm Hg and/or diastolic BP 90 mm Hg or greater at Treatment/Day 0 (can repeat 15 minutes later to confirm)
- 11. Beck Depression Inventory (BDI-II) score >24 at screening

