3.6.4 Vital Signs, Physical Findings and Other Observations Related to Safety

3.6.4.1 Vital Signs

The observed data at baseline and change from baseline for each measurement day will be summarized with descriptive statistics. A plot of average vital sign parameters will be presented over time.

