3.6.4.3 Electrocardiogram Results

The observed data at baseline and change from baseline for each measurement day will be summarized with descriptive statistics by treatment group.

The overall ECG assessment based upon PI assessment will be summarized including post treatment ECGs determined to be abnormal clinically significant.

35

The absolute QTcF values provided by the core lab will be analyzed as a categorical variable. Each QTcF value in a given patient will be grouped into 4 categories:

- QTcF interval < 450 msec
- QTcF interval 450 480 msec
- QTcF interval > 480 500 msec
- QTcF interval > 500 msec

The changes in QTcF measures will also be analyzed as categorical variables. The change in QTcF in a given patient will be grouped into 2 categories:

- QTcF interval increases from baseline > 30 msec
- QTcF interval increases from baseline > 60 msec

The overall ECG assessment will be summarized along with a summary of how many subject developed a post treatment abnormal clinically significant result. Denominators for percentages will use the number of assessments available at each visit.

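### The plan does not tabulate how many subjects on each dose had a marked blood pressure rise, or how large laboratory abnormalities were

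*Protocol*

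**What the plan says.** **Blood pressure.** Protocol 13.4.4.5 plans: "The observed data at baseline and change from baseline for each measurement day will be summarized with descriptive statistics". SAP 3.6.4.1 repeats this and adds: "A plot of average vital sign parameters will be presented over time". Descriptive statistics are defined in Protocol 13.4: "Continuous variables will be summarized with mean, median, standard deviation, minimum, and maximum"; SAP 3.1 lists the same measures. Neither document plans a count of subjects above a BP level or with a BP change of a given size.

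**Laboratory values.** Protocol 13.4.4.3 and SAP 3.6.3 plan summary statistics by visit and two categorical outputs: "Subjects with clinical laboratory values outside of the normal reference range at any post-baseline assessment will be summarized" and "Shifts from baseline clinical laboratory values based upon the normal range and will be tabulated". The SAP adds plots of averages. There are no multiples of ULN, grades or marked-abnormality limits.

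**QTcF.** SAP 3.6.4.3 takes a different approach: "The absolute QTcF values provided by the core lab will be analyzed as a categorical variable". It uses cut-points at 450, 480 and 500 msec and counts increases above 30 and above 60 msec.

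**Collection.** Under the Schedule of Events, vital signs are taken at every visit, and both before and 4 hours after dosing on Day 0 and at Weeks 12, 24 and 36. SAP 2.3 (Table 2) selects one value per window, the one closest to the target day, and gives ties to the first observation.

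**The concern.** Comparing safety with placebo is a stated secondary objective. The protocol itself supplies reasons to look at BP subject by subject. Protocol 5.2 says of CGRP, the molecule ALD403 binds: "It is the most potent peptide vasodilator and can function in the transmission of pain". Protocol 8.2 excludes hypertension (criterion 7) and, in criterion 10, "Systolic blood pressure (BP) 140 mm Hg and/or diastolic BP 90 mm Hg or greater at Treatment/Day 0". Nearly every subject therefore starts below a limit that the protocol set, so later crossings could be counted cleanly.

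A rise confined to a few percent of an arm is diluted in the arm mean. What is at stake is whether the report will show how many subjects had a marked rise on each dose and on placebo.

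For laboratory values the loss is magnitude: a value just above the reference limit counts the same as a several-fold rise. Protocol 8.2 criterion 9 sets its ALT and AST limit at 2 x ULN, so a subject may enter just under that. If such a subject rises to, say, 5 x ULN, the shift table reads high-to-high, exactly as for a subject who stayed put.

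**Working it through.** **1. Arm size.** The documents state no figure for detecting safety outliers, so the only design figure to reproduce is the efficacy power at 200 per group. Power = Φ(δ / (σ√(2/200)) − 1.96). With δ = 1 and σ = 2.7: 1/0.27 − 1.96 = 1.74, giving 95.9% (stated: at least 95%). With σ = 3: 1/0.30 − 1.96 = 1.37, giving 91.5% (stated: 90%). The arm size of 200 is used below.

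**2. Assumptions (not in the documents).** Baseline SBP mean 118, SD 11, truncated below 140; SD of change s = 8 to 12 mmHg; a fraction f = 5% of one ALD403 arm has an extra rise R = 25 to 35 mmHg.

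**3. Comparison of means.** Mean shift = fR = 0.05 × 25 = 1.25, up to 0.05 × 35 = 1.75 mmHg. Variance of change in the affected arm = s² + f(1−f)R². SE = √[(s² + s² + f(1−f)R²)/200].
- s = 12, R = 25: √[(288 + 29.7)/200] = 1.26; 1.25/1.26 = 0.99; power Φ(0.99 − 1.96) = 17%.
- s = 8, R = 35: √[(128 + 58.2)/200] = 0.965; 1.75/0.965 = 1.81; power Φ(1.81 − 1.96) = 44%.

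Simulation over the whole range gives 16-46%.

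**4. Counts, same model.** The scheduled readings after the first infusion number 14: ten visits (Weeks 4, 8, 12, 16, 20, 24, 28, 36, 48, 56) plus four 4-hour readings. Any two readings are assumed correlated 0.3 to 0.7 and, for the repeated-reading rows, the rise is sustained. Ranges are from simulation with z-tests and carry an error of a few points.

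| Measure, 5% affected | Power |
|---|---|
| Means at one reading | 16-46% |
| SBP ≥140 with rise ≥20, one reading | 23-85% |
| Same, confirmed at two consecutive readings | 26-93% |
| Same, at any of 14 readings | 11-61% |
| SBP ≥140 alone, one reading | 13-38% |
| SBP ≥140 alone, any of 14 readings | 9-24% |

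The combined one-reading count is about 6-13 affected-arm subjects against 1-6 on placebo. SBP ≥140 alone at any of 14 readings flags about 23-69 of 200 placebo subjects and does worse than means in every setting. The combined any-reading count beats means at s = 8 but is about equal or worse at s = 10 to 12. With 3% affected, means have 8-20% power and the combined one-reading count 12-55%.

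**5. What the printed maximum shows.** With 5% of an arm rising 30 mmHg and s = 8 to 15, the expected arm maximum of change goes from 22-41 to 42-54 mmHg. It exceeds the 95th percentile of an unaffected arm's maximum in 55-100% of simulated trials. It reveals an extreme subject, not how many there are.

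**6. Laboratory background.** There are seven post-baseline draws (Weeks 4, 12, 24, 28, 36, 48, 56). With a 95% reference range and independent draws, the chance that an unaffected subject is ever out of range is 1 − 0.95⁷ = 30% per analyte; on the high side it is 1 − 0.975⁷ = 16%. At within-subject correlation 0.9 these fall to 11% and 6%.

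**7. Post-infusion readings.** Trial day is computed from dates, so the pre-dose and 4-hour readings on a dosing day are equally far from target. Read literally, the Table 2 tie rule keeps the pre-dose reading and leaves the 4-hour reading out of the by-visit summary. The SAP does not say whether post-dose readings are summarised separately.

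**The case against.** A reader might infer that a marked rise in a minority would leave no trace, or that the trial could not state how many subjects became hypertensive. The documents do not support either reading. Minimum and maximum are printed. Shift tables condition on baseline status, so moves from normal to high are visible. Asymptomatic findings that the investigator judges clinically significant become adverse events (Protocol 11.1.2) and are tabulated by arm. A DMC reviews safety. Every reading is collected, so the count could be produced later; it is simply not pre-specified.

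The biological rationale also has another side. Protocol 5.3.1 reports no ALD403-related blood pressure change in the six-month monkey study. Protocol 5.3.3 puts exposure at 300 mg at least 56-fold (Cmax) and 19-fold (AUC) below that at its no-effect level. Protocol 5.4 reports no toxicity identified from CGRP blockade.

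The 140/90 and criterion 9 limits are entry limits, and the ≥20/≥10 mmHg and ≥3 x ULN cut-offs appear nowhere in the documents. With Fisher's exact test the power advantage of the count shrinks and sometimes disappears.

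All of this stands, and it confines the point to reporting. None of it supplies the number of subjects affected or the size of laboratory rises, and the adverse-event route depends on judgement across about 85 centers.

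**Conclusion.** The point holds as a reporting gap against a stated safety objective. Neither document plans a per-subject BP threshold count or a graded laboratory count, although the SAP does this for QTcF. The sponsor should close it; efficacy conclusions and alpha are untouched.

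The power figures rest on an assumed BP distribution, rise and affected fraction. They support a combined level-and-change count at a given reading, or a confirmed one. They do not support counting any single reading of 140/90 or more, which over 14 scheduled readings is mostly background. The advantage is clear at an SD of change of 8 mmHg and modest at 12. The stronger argument is that the numbers affected would be visible by dose.

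**What to change.** **SAP 3.6.4.1 (and Protocol 13.4.4.5).** By dose, and for all ALD403 combined, against placebo, with risk difference and 95% CI, report the number and percent of subjects meeting a combined criterion, for example SBP ≥140 with a rise ≥20, or DBP ≥90 with a rise ≥10 mmHg. Do this at each measurement time, with pre-dose and 4-hour post-infusion readings shown separately. Add a count confirmed at two consecutive readings, and state whether same-day pre- and post-dose readings count as consecutive. The by-time table is needed as well because a confirmed count can miss a transient post-infusion rise. Do not use an unconfirmed any-reading ≥140/90 count. State in SAP 2.3 how 4-hour readings are handled under Table 2.

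**SAP 3.6.3 (and Protocol 13.4.4.3).** Add graded counts shown by baseline status, for example ALT or AST ≥2 x and ≥3 x ULN, and the criterion 9 limits: hemoglobin <10 g/dL, ANC <1000 cells/μL, platelets <100,000 cells/μL, creatinine >2.0 mg/dL.

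These are analysis categories only, not rules for managing subjects. The cost is SAP wording and a few tables from data already collected. The downside is a few more descriptive safety comparisons, some of which will differ by chance.
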